3.2. Exclusion Criteria

Patients who meet any of the following criteria will be excluded from study entry:

1. Clinical laboratory values meeting the following criteria within 4 weeks (28 days) prior to baseline:
 - a. Serum creatinine $\geq 1.5 \times$ upper limit of normal (ULN) AND calculated creatinine clearance ≤ 60 mL/min using Cockcroft-Gault equation.
 - b. Total bilirubin $\geq 1.5 \times$ ULN or $\geq 3.0 \times$ ULN in the presence of documented Gilbert's syndrome.
 - c. Aspartate aminotransferase or ALT $\geq 2.5 \times$ ULN, or AST or ALT $\geq 5.0 \times$ ULN in the presence of liver metastases.
 - d. Hematologic function:
 - i. Absolute neutrophil count (ANC) ≤ 1000 cells/ μ L.

- ii. Hemoglobin \leq 8.5 g/dL or 5.28 mmol/L.
- iii. Platelet count \leq 75,000/ μ L.

2. Significant cardiovascular disease, including:
 - a. Cardiac failure New York Heart Association Class III or IV ([Appendix D](#)), or left ventricular ejection fraction (LVEF) $<$ 50% or below the lower limit of the Institution's normal range.
 - b. Myocardial infarction, severe or unstable angina within 6 months prior to baseline.
 - c. Significant thrombotic or embolic events within 3 months prior to baseline including, but not limited to, stroke or transient ischemic attack. Catheter-related thrombosis and deep vein thrombosis are not a cause for exclusion.
 - d. History or presence of any uncontrolled cardiovascular disease.
 - e. Personal or family history of long QT syndrome.
3. ECG findings obtained using the study site's ECG machine-derived measurements, meeting any of the following criteria:
 - a. Evidence of second- or third-degree atrioventricular block.
 - b. Clinically significant arrhythmia (as determined by the Investigator).
 - c. QTc interval of $>$ 470 msec as calculated according to Fridericia's formula (QTcF = QT/R to R interval^{0.33}).
4. Leptomeningeal or untreated central nervous system (CNS) malignancies (primary or metastatic); patients with asymptomatic CNS metastases who have undergone surgery or radiotherapy 4 weeks prior to C1D1 and who are on a dose of prednisone of no more than 10 mg or equivalent will be eligible for **Part A** of the trial.
5. Received other recent antitumor therapy, including:
 - a. Investigational therapy administered within the 28 days prior to baseline or 5 half-lives, whichever is shorter.
 - b. Any standard chemotherapy, targeted therapy (TKI or mAB), or radiation within 14 days prior to baseline.

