4.3.2. Dose-limiting Toxicity

Toxicity will be assessed using the NCI [CTCAE Version 5.0](#) unless otherwise specified.

A toxicity will be considered dose-limiting (unless clearly attributable to an extraneous cause, such as underlying disease) if it occurs during the first cycle (21 days) of treatment with BDTX-189. Dose-limiting toxicities (DLTs) will be defined as follows:

- Any death not clearly due to the underlying disease or extraneous causes.
- Hematologic toxicity
 - Grade 4 neutropenia or thrombocytopenia for >7 days or febrile neutropenia.
 - Grade 3 thrombocytopenia associated with bleeding or requiring a platelet transfusion.
 - Grade ≥ 4 anemia.
- Non-hematologic toxicity of \geq Grade 3 (at any time during treatment) that, in the judgment of the Investigator, is dose-limiting except for:
 - Grade 3 fatigue lasting <1 week.
 - Grade 3 nausea, vomiting, or diarrhea lasting <5 days without adequate supportive care.

- Grade 3 nausea, vomiting, or diarrhea lasting <24 hours with adequate supportive care.
- The following non-hematologic laboratory abnormalities:
 - Baseline Grade ≤ 1 ALT or AST: any drug -related Grade ≥ 3 abnormality of ALT and/or AST or increase in ALT or AST $>3 \times$ ULN with a concurrent increase in total bilirubin $>2 \times$ ULN (per Hy's Law).
 - Baseline Grade ≥ 2 ALT or AST due to liver metastases: any drug-related ALT and/or AST $>2 \times$ baseline or $\geq 10 \times$ ULN.
- Dose reduction during Cycle 1 due to an AE related to BDTX-189.
- Delay of starting Cycle 2 for >2 weeks if due to an AE related to BDTX-189.
- Interruption of BDTX-189 dosing for more than 7 days during Cycle 1, if due to a drug-related AE.

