4.3.5. Dose Modifications

If toxicity occurs, the toxicity will be graded using the NCI [CTCAE Version 5.0](#), and appropriate supportive care treatment will be administered to decrease the signs and symptoms thereof. Dose adjustments will be based on the organ system exhibiting the greatest degree of toxicity.

Specific criteria for interruption, re-initiation, dose reduction, and/or discontinuation of BDTX-189 are listed in [Table 8](#). All interruptions or modifications must be recorded on the AE and drug administration eCRFs. Appropriate clinical experts must be consulted as deemed necessary.

The Investigator will evaluate which AEs are attributed to the study drug and adjust the dose of the drug as recommended below. All dose modifications must be based on the worst preceding toxicity ([CTCAE Version 5.0](#)).

Patients whose treatment is delayed due to AEs may continue treatment if the AE resolves within 21 days of onset. Any patient who requires a treatment interruption of more than 21 days due to AEs will be discontinued from study treatment unless the Investigator and the Medical Monitor agree that continued treatment at the appropriate dose is in the best interest of the patient.

A maximum of 2 dose reductions are allowed in this study. [Table 7](#) outlines acceptable dose reductions for patients in the Safety Expansion of Part A or Part B, who are enrolling after the implementation of Amendment 3. Once the dose of BDTX-189 has been reduced because of toxicity, all subsequent cycles must be administered at that lower dose level unless further dose reduction is required. The patient will be withdrawn from study treatment if further toxicity meeting the requirement for dose reduction occurs. Dose reduction below the initial starting dose levels for QD and BID in Part A, respectively, is not allowed. Otherwise, the patient must be removed from treatment.

Recommended BDTX-189 dose modifications are presented in [Table 8](#).

Table 7 Dose Reduction Levels for BDTX-189 Administered Once or Twice Daily

Original dose	800 mg QD	400 mg BID
Dose level -1	600 mg QD	300 mg BID

Dose level -2	400 mg QD	200 mg BID
---------------	-----------	------------

Table 8 Dose Modification Guidelines for BDTX-189-related Adverse Events

Recommended Dose Modifications	
Worst toxicity NCI CTCAE v5.0 Grade (value)	Recommended dose modification any time during a cycle of therapy
Renal	
Serum creatinine	
≤1.5 × ULN	Maintain dose level

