Grade 2 (>1.5 to 3 × ULN)	Omit dose until resolved to baseline, then 
 • If resolved ≤ 7 days, then maintain dose level • If resolved > 7 days, then ↓ 1 dose level
Grade 3 (>3.0 to 6.0 × ULN)	Discontinue patient from study treatment
Grade 4 (>6.0 × ULN)	Discontinue patient from study treatment
Hepatic	
Total bilirubin	
<1.5 × ULN	Maintain dose level
Grade 2 (>1.5 to 3 × ULN if baseline was normal; >1.5 to 3.0 × baseline if baseline was abnormal)	Omit dose until resolved to baseline, then 
 • If resolved ≤ 7 days, then maintain dose level • If resolved > 7 days, then ↓ 1 dose level
Grade 3 (>3.0 to 10.0 × ULN if baseline was normal; >3.0 to 10.0 × baseline if baseline was abnormal)	Omit dose until resolved to baseline, then 
 • If resolved ≤ 7 days, then ↓ 1 dose level • If resolved > 7 days and discontinue patient from study treatment
Grade 4 (>10.0 × ULN if baseline was normal; >10.0 × baseline if baseline was abnormal)	Discontinue patient from study treatment Note: If Grade 3 or 4 hyperbilirubinemia is due to the indirect (unconjugated) component only and hemolysis has been ruled out as the etiology as per institutional guidelines (e.g., review of peripheral blood smear and haptoglobin determination), then ↓ 1 dose level and continue treatment at the discretion of the Investigator
AST or ALT	
Grade 1 (>ULN to 3.0 × ULN if baseline was normal; >1.5 to 3.0 × baseline if baseline was abnormal)	Maintain dose level
Grade 2 (>3.0 to 5.0 × ULN if baseline was normal; >3.0 to 5.0 × baseline if baseline was abnormal)	Maintain dose level
Grade 3 (>5.0 to 20.0 × ULN if baseline was normal; >5.0 to 20.0 × baseline if baseline was abnormal)	Omit dose until resolved to ≤ Grade 1 (or ≤ Grade 2 if liver metastases present), then either maintain dose level (if Grade 3 lasted ≤ 7 days) or ↓ 1 dose level (if Grade 3 lasted > 7 days)
Grade 4 (>20.0 × ULN if baseline was normal; >20.0 × baseline if baseline was abnormal)	Discontinue patient from study treatment

Recommended Dose Modifications

Worst toxicity NCI CTCAE v5.0 Grade (value)	Recommended dose modification any time during a cycle of therapy
Combination of bilirubin and AST/ALT	

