9.5.5. Safety Analysis

Safety will be assessed through the analysis of the reported incidence of TEAEs. Treatment emergent AEs are those with an onset on or after the initiation of therapy (on or after C1D1, first dose of study drug) and will be graded according to NCI [CTCAE Version 5.0](#).

The TEAEs will be coded using the current version of Medical Dictionary for Regulatory Activities (MedDRA; <https://www.meddra.org/about-meddra/>) and summarized using system organ class and preferred term for all patients in the FA population. In addition, summaries of SAEs, TEAEs leading to treatment discontinuation, TEAEs by maximum NCI CTCAE grade, and TEAEs related to study treatment will also be presented. TEAEs will be summarized separately for Part A and Part B. In Part A, the TEAE summary will be provided by dose level, cohort, and overall, whereas in Part B, the TEAE summary will be provided by cohort, subgroups within a cohort (as appropriate), and overall. Additional TEAE analysis (such as subset or pooled analysis) could be performed if data warrants.

Other safety endpoints including laboratory results, vital signs, physical examinations, ECG findings, and cardiac function will be summarized for all patients in the FA population and presented separately for Parts A and B, respectively. Descriptive summary statistics of observed values, as well as changes from baseline, will be presented. In addition, laboratory parameters will also be summarized by shift from baseline CTCAE grade to maximum post-baseline CTCAE grade ([NCI CTCAE Version 5.0](#)).

Concomitant medications will be coded using the World Health Organization Drug Dictionary (WHO DD; <https://www.who-umc.org/>) and they will be listed and summarized for Part A and Part B separately.

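### Section 9.5.5's CTCAE v5.0 grade shifts understate liver-test worsening in patients whose baseline ALT, AST or bilirubin is abnormal, because their post-baseline grade is set by their own baseline

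*Combined protocol and SAP*

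**What the plan says.** Section 9.5.5 plans, for the full analysis population, that "laboratory parameters will also be summarized by shift from baseline CTCAE grade to maximum post-baseline CTCAE grade", using CTCAE v5.0. It also plans descriptive summaries of observed values and of changes from baseline. It gives no rule for a patient whose baseline is already abnormal, and does not say on what scale the baseline grade is assigned.

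The cut-offs appear in Table 8 (Section 4.3.5), in a column headed "Worst toxicity NCI CTCAE v5.0 Grade (value". For AST or ALT they are:

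- "Grade 1 (>ULN to 3.0 × ULN if baseline was normal; >1.5 to 3.0 × baseline if baseline was abnormal"
- "Grade 2 (>3.0 to 5.0 × ULN if baseline was normal; >3.0 to 5.0 × baseline if baseline was abnormal"
- "Grade 3 (>5.0 to 20.0 × ULN if baseline was normal; >5.0 to 20.0 × baseline if baseline was abnormal"

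Grade 4 follows the same pattern above 20 times. For total bilirubin, the first band relative to baseline is "Grade 2 (>1.5 to 3 × ULN if baseline was normal; >1.5 to 3.0 × baseline if baseline was abnormal"; Table 8 has no such band at Grade 1.

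Two other sections show that abnormal baselines are expected. Exclusion 1c sets its higher AST/ALT limit at 5.0 × "ULN in the presence of liver metastases", so values just below that can be enrolled. Section 4.3.2 has a DLT criterion for patients already at Grade 2 or above at baseline. It reads in part "ALT or AST due to liver metastases: any drug-related ALT and/or AST", with limits of more than 2 × baseline or at least 10 × ULN.

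**The concern.** A shift table can be read only if both axes use the same scale. With an abnormal baseline, the post-baseline grade measures the multiple of that baseline, not the absolute level. The baseline grade cannot be on that scale in any informative way, because every baseline is 1 × itself. Section 4.3.2 speaks of patients at baseline Grade 2 or above, and such patients exist only if baseline is graded against ULN.

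At stake is the categorical liver-safety summary. Section 1.1.7 reports increased ALT as a TEAE in 23.1% of 65 treated patients (about 15) and at Grade 3 or above in 7.7% (about 5). Sections 1.1.7 and 1.2.1 list ALT/AST increases among the observed DLTs. These rates are not specific to patients with an abnormal baseline, but they show that the liver is an organ of interest for this drug.

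**Working it through.** The plan gives no figure to reproduce. The check applies its own cut-offs to values that eligible patients can have.

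**Inputs.** Let b be baseline and x the maximum post-baseline value, both in multiples of ULN, and let r = x/b.

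- Grade on the ULN scale (Table 8, normal-baseline wording): 1 if above 1 to 3; 2 if above 3 to 5; 3 if above 5 to 20; 4 above 20.
- Grade with an abnormal baseline (Table 8): 1 if r is above 1.5 to 3; 2 if above 3 to 5; 3 if above 5 to 20; 4 above 20; ungraded (0) at 1.5 or below.
- DLT limits for baseline Grade 2 or above (Section 4.3.2): x > 2b or x ≥ 10, if drug-related.
- Eligible Grade 2 baseline (exclusion 1c): above 3 to below 5 × ULN, with liver metastases.

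**Worked case, b = 4 (Grade 2 on the ULN scale).**

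| Rise to (× ULN) | r | DLT limits met | Baseline on ULN scale | Baseline against itself | ULN scale at both times |
|---|---|---|---|---|---|
| 10 | 10/4 = 2.5 | both | 2 to 1 | 0 to 1 | 2 to 3 |
| 16 | 16/4 = 4 | both | 2 to 2 | 0 to 2 | 2 to 3 |
| just above 20 | > 5 | both | 2 to 3 | 0 to 3 | 2 to 4 |

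**General case.** For an eligible Grade 2 baseline, 2b is below 10, so the DLT limit is first passed at 2b. That point lies inside the Grade 1 band (above 1.5b to 3b). With baseline on the ULN scale:

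| b | Shown as 2 to 1 although past the DLT limit (above 2b to 3b) | Shown as 2 to 2 (above 3b to 5b) | Shown as worse (above 5b) |
|---|---|---|---|
| 3.1 | 6.2 to 9.3 | 9.3 to 15.5 | > 15.5 |
| 4 | 8 to 12 | 12 to 20 | > 20 |
| 4.9 | 9.8 to 14.7 | 14.7 to 24.5 | > 24.5 |

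With the ULN scale at both time points, every value past the DLT limit exceeds 2 × 3 = 6 × ULN. It is therefore Grade 3 or 4 and is shown as worsening.

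**Baseline graded against itself.** Here r = 1 at baseline, so every abnormal baseline becomes Grade 0. The rise from 4 to 10 × ULN is then shown as worsening, but it falls in the same cell (0 to 1) as a normal baseline rising to anywhere between 1 and 3 × ULN. This reading also leaves the Section 4.3.2 category empty.

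**Without liver metastases.** A baseline of 2 × ULN is eligible (the limit is 2.5). A rise to 6 × ULN gives r = 3, shown as 1 to 1 with baseline on the ULN scale. The same 6 × ULN after a normal baseline is Grade 3.

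**Bilirubin.** The effect is narrower. An eligible baseline above 1.5 × ULN requires Gilbert's syndrome (limit 3.0). A rise from 2.5 to 3.7 × ULN gives r = 1.48, below the Grade 2 floor of 1.5, although both values are Grade 2 or above on the ULN scale (2 to 3).

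**The case against.** The strongest reply is that Section 9.5.5 does not say how baseline is graded and does not cite Table 8, which is a dose-modification guide. Section 9.1 leaves further detail to the SAP. A programmer might grade both time points against ULN, and the problem would disappear. This reply stands in part: a reader might infer that hepatic DLTs will be tabulated as improvements, and the documents do not support that without conditions. The reversal needs the ULN-scale baseline that Section 4.3.2 implies, and a Grade 2 baseline. What remains is that the v5.0 grading the plan names, as the protocol sets it out, understates the level reached on either reading, and that the supplied text has no rule putting both time points on the ULN scale.

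The second reply is that the liver signal is captured elsewhere. Observed values and changes from baseline are summarised, DLTs are counted by their own criteria, and Section 8.2.4 requires immediate notification of potential Hy's Law cases on ULN limits. This is right, and a reader should not infer that the signal is lost. The cover is partial, however. Averages dilute individual elevations. DLT counts cover Part A Cycle 1 only, with at most 60 DLT-evaluable patients excluding titration, and not the approximately 491 patients of Part B. Hy's Law needs bilirubin of at least 2 × ULN as well, so isolated transaminase rises fall outside it. The planned TEAE summary by maximum grade uses the same v5.0 grading.

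A reader might also infer that the SRC or DMC will decide from this table. The documents do not say so: Section 10.3.1 has the SRC review all available safety information, and Section 10.3.2 leaves DMC detail to a charter.

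**Conclusion.** The point holds in limited form. For patients with abnormal baseline ALT or AST, the planned v5.0 grade shift understates hepatic worsening whichever way baseline is graded. At baseline 4 × ULN, a rise to 10 × ULN appears as 2 to 1 or 0 to 1, against 2 to 3 on a common ULN scale. With baseline on the ULN scale, a rise to 16 × ULN appears as no change, and worsening appears only above 20 × ULN. Bilirubin is affected from Grade 2 up; an apparent improvement there requires a baseline of the Gilbert's type.

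The result assumes that Table 8 is the v5.0 grading to be used in Section 9.5.5, as its column label indicates. An apparent improvement in a patient who meets the DLT limits for baseline Grade 2 or above further assumes a ULN-scale baseline of more than 3 to less than 5 × ULN, which is eligible only with liver metastases.

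The number of patients affected cannot be derived. The documents give no proportion with abnormal baseline liver tests, and applying an assumed proportion to all 619 planned patients would overstate the reversal, which needs the smaller Grade 2 subset. This is a distortion in one safety table that should be corrected; it does not remove liver safety monitoring from the trial.

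**What to change.** In Section 9.5.5:

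- Present ALT, AST and total bilirubin shifts in multiples of ULN at both baseline and maximum post-baseline, in place of or alongside the v5.0 grade shift. Possible categories are ≤1, >1 to 3, >3 to 5, >5 to 10, >10 to 20 and >20 for ALT/AST, and ≤1, >1 to 1.5, >1.5 to 2, >2 to 3 and >3 for bilirubin.
- State the scale used for the baseline grade wherever a grade shift is kept.
- List the maximum multiple of baseline for each patient with an abnormal baseline, so that the relative change remains visible.

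The DLT and dose-modification rules are unchanged and no new data are collected. The cost is SAP wording and table programming, and a liver table that may look slightly less favourable.

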9.5.6. Pharmacokinetics

Plasma concentrations of BDTX-189 will be used to calculate the PK parameters. The plasma PK parameters to be analyzed include $AUC_{0-\infty}$, $AUC_{(0-t)}$, C_{max} , T_{max} , and $t_{1/2}$. These parameters will be listed by individual patient and summarized by descriptive statistics (means, medians, ranges, standard deviations, geometric means, 90% CI, and coefficients of variation) as appropriate, by treatment group/cohort. Pharmacokinetic parameters will be analyzed separately for Dose Escalation and the Food-Effect Cohort.

For the Food-Effect Cohort, the following exposure measures and PK parameters will be derived and reported: $AUC_{0-\infty}$, AUC_{0-t} , C_{max} , T_{max} , t_{lag} , $t_{1/2}$, Cl/F , and Vd/F . Individual patient measurements as well as summary statistics (e.g., group averages, standard deviation, coefficients of variation, ranges) will be reported. Exposure measurements (AUC and C_{max}) will be log-transformed. When the 90% CI for the ratio of the log-transformed population geometric means of either $AUC_{0-\infty}$ (AUC_{0-t} when appropriate) or C_{max} between fed and fasted treatments fails to meet the limits of 80 – 125%, specific recommendation on the clinical significance of the food effect will be provided. The clinical relevance of any difference in T_{max} and t_{lag} will be described.

Population PK parameters including Cl/F , Vd/F , and K_a will also be used to investigate the PK of BDTX-189 in Part B. Oral clearance will be used to generate estimates of BDTX-189 AUC.

Further details on the PK analyses will be documented in a separate PK analysis plan.

9.5.7. Biomarkers

On-treatment paired tumor tissue will be evaluated for changes from baseline to C2D1 in pathway signaling downregulation (e.g., ERK phosphorylation) and potential mechanisms of resistance or evidence of alternative pathway activation at the time of tumor progression (e.g., PI3K/AKT and co-occurring genomic alterations).

Blood samples collected for ctDNA extraction will be analyzed for the relationship between changes in allosteric mutations, tumor mutational burden and response to treatment. In addition, innate and acquired resistance mechanisms may be explored. Markers tested may include, but will not be limited to, allosteric *ErbB* mutations, [REDACTED] mutations (e.g., [REDACTED]), and alterations in other genes involved in [REDACTED] and [REDACTED] signaling. Similarly, the relationship between other blood-borne biomarkers and drug response and/or disease progression may be explored.

9.5.8. Quality of Life

Quality of life data will be collected via ePROs. The questionnaire data from FACT-G, NCCN FACT FBSI-16, NCCN-FACT FLSI-17, EQ-5D-5L, and Physical Function PROMIS Short Form will be scored according to the corresponding scoring manual for each questionnaire. The responses from each NCI-CTCAE question will be assessed individually. Descriptive statistics will be used to summarize the scores at each visit as well as the change from baseline over time. In addition, the change from baseline values for some scores may be assessed in a longitudinal manner using a mixed-effect model for repeated measures.

9.6. Analysis Time Points

9.6.1. Final Analysis

The final analysis for a given cohort in Part B will occur once all patients in the cohort are enrolled and have either been treated for at least 6 months or discontinued treatment for any reason prior to 6 months after their first dose of study drug.

The final analysis of the entire study will occur after all patients have discontinued the study (Part A will be separate from Part B).

9.6.2. Planned Interim Analysis

To minimize exposing patients that may be unresponsive to BDTX-189 therapy in Part B, the plan is to apply the stopping rules described in Section 9.6. The interim analysis for each cohort will be conducted once the required number of patients have been enrolled and have either undergone at least 1 postbaseline tumor assessment or discontinued treatment for any reason prior to their first postbaseline tumor assessment.

10. QUALITY ASSURANCE AND QUALITY CONTROL

10.1. Monitoring

Site monitoring shall be conducted to ensure that patient protection, study procedures, laboratory, study intervention administration, and data collection processes are of high quality and meet Sponsor, Good Clinical Practice (GCP), ICH and, when appropriate, regulatory guidelines.

